10.2 Population to be analysed

Clinic-referred older adults with multi-domain amnesic MCI with sleep disturbance.

10.3 Statistical Analysis Plan

Phase I: An *intention-to-treat* approach using recommended Linear Mixed Modelling⁴ will evaluate a model including main effects for Group (Arm A vs Arm B), Time (BL vs FU1) and the main interaction term of interest: Group X Time. Covariates will only be added if baseline differences are noted between groups.

Phase II Linear Mixed Modelling⁴ will evaluate a model including main effects for Group (Arm A vs Arm B), Time (Arm A BL vs FU1, Arm B **FU1 vs FU2**) and the main interaction term of interest: Group X Time. An additional covariate of initial global cognitive status will be added to this analysis to control for different potential starting points for the two arms at the different timepoints.

Phase III: Equivalence of the two arms at follow up III will be tested using a two one-sided test (TOST⁴²).

Clinical Response Prediction will be addressed by multiple regression examining relationships between baseline predictor variables (i.e; cognitive profile) and cognitive change scores.

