	
Subjects will be randomly allocated in a 1:1 ratio to either 3-months of supervised, centre-based, multidomain CCT (ARM A) or wait-list control. The main endpoint from Phase I will be to determine whether CCT is effective for improving overall cognition for those with multidomain MCI with sleep disturbance. This is the trial’s primary outcome.
 
The Phase II endpoint is to assess whether the magnitude of therapeutic effect is dependent on the onset of treatment. Arm A started CCT 3-months prior and will transition to no-contact follow-up for 3-months, whilst Arm B that was on-hold for 3-months will commence the identical CCT intervention that Arm A completed in Phase I.
 
The endpoint for Phase III is to determine whether delayed start of CCT matters after a period of no-contact follow up. The trajectory of cognitive function following early intervention versus delayed intervention will be examined. Both groups will receive no intervention for a further 3 months, with the main difference being that Arm A halted CCT 3-month previously whilst Arm B started CCT 3-months later. In order to assess the effect of delayed start separately from waning of benefits, Arm A at the end of Phase I will be compared to Arm B at the end of Phase II. Arm A at the end of Phase II will also be compared to Arm B at the end of Phase III to investigate the effect of delayed start on longevity of the intervention.
 
Cognitive assessment will be completed at baseline and at the end of each phase.

Statistical Procedures Sample Size Calculation: Analysis Plan:
	
 • Phase I: An intention-to-treat approach using recommended Linear Mixed Modelling⁴ will evaluate a model including main effects for Group (Arm A vs Arm B), Time (BL vs FU1) and the main interaction term of interest: Group X Time. Covariates will only be added if baseline differences are noted between groups. • Phase II Linear Mixed Modelling⁴ will evaluate a model including main effects for Group (Arm A vs Arm B), Time (Arm A BL vs FU1, Arm B FU1 vs FU2) and the main interaction term of interest: Group X Time

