The Winblad 2004²² recommends the diagnosis of MCI to fulfil the following criteria: 1. The individual does not meet the criteria for a dementia syndrome in accordance to the DSM IV or ICD 10; 2. Functional activities of the person are mainly preserved; 3. Evidence of cognitive decline.

Objective cognitive impairment is defined as performance of more than or equal to 1.5 standard deviation below the patient's estimated level of premorbid general intellectual functioning (determined using the Wechsler Test of Adult Reading²³).

Cognitive domains are defined based on the following:

Memory: Wechsler Adult Intelligence Scale (WAIS) Digit Span²⁴; Rey Auditory Verbal Learning Test²⁵; Wechsler Memory Scale-III Logical Memory I²⁶ and II²⁷,

Learning: Rey Complex Figure Test-3 minute Recall²⁸,

Speed of processing: Trails Making A²⁹

Language: Controlled Oral Word Association Test³¹; Boston Naming Test³¹

Visuospatial skills: Rey Complex Figure Test-Copy²; Clock-drawing Test³³

Executive functioning: Delis Kaplan Executive Functioning System^a (STROOP)³⁴; Trails Making B²⁹;

Daily function: Amsterdam IADL (informant-rated if available)³⁴, Global Deterioration Scale³⁵; Global assessment of Functioning Scale³⁷

Where possible, alternate forms are used between assessments to reduce retest effects.

Single domain MCI refers to MCI with impairment in only one domain; if more than one domain is affected, it is defined as **multi-domain MCI**. Amnesic MCI is defined here by an impairment in delayed recall (assessed as Logical Memory II total score or percent retention²⁷; Rey Auditory Verbal Learning Test trial 7 total score or 7/5 percent retention²⁵). In cases where only new learning is impaired but delayed recall is intact, the individual is categorised as non-amnesic MCI.

Sleep disturbance criteria

Sleep disturbance will be measured with the Pittsburg Sleep Quality Index (PSQI)²⁰: Self Report Questionnaire. Patients with multi-domain MCI diagnosed with the above criteria and a score of ≥ 5 in the PSQI; without any major neurological or psychiatric disorder, major depression, current alcohol abuse, will be eligible for the study.

^a If this test data is not available/provided by the referral memory clinic we will conduct the test after consent and prior to commencement of the intervention

Randomisation

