5.4 Excluded medications and treatments

Participants currently undertaking any 3rd generation antidepressants that are SSRIs or tricyclic antidepressants and with current symptoms of depression, and those currently undertaking other CCT program(s).

6. PARTICIPANT ENROLMENT AND RANDOMISATION**6.1 Recruitment**

62 older adults diagnosed with multi-domain amnesic MCI with sleep disturbance will be recruited from the Healthy Brain Ageing Clinic, Brain and Mind Centre and POWH Memory Clinic in a rolling fashion. The clinics accept referrals from neurologists, geriatricians and psychiatrist as well as local GPs for aged individuals who report new onset cognitive problems. Most of the baseline tests will be taken as part of standard clinic assessment; accordingly, these data will need to have been collected within the last 6-months in order to be valid for study entry.

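### Phase II compares different test occasions in the two arms, so a timing effect cannot be separated from retest gain and regression to the mean, and the added covariate does not correct this

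*Protocol*

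**What the plan says.** The protocol synopsis and section 10.3 define the Phase II model in the same way: "Time (Arm A BL vs FU1, Arm B FU1 vs FU2) and the main interaction term of interest: Group X Time". Section 10.3 alone adds a covariate: "An additional covariate of initial global cognitive status will be added to this analysis to control for different potential starting points".

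Four other statements bear on this model:

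- **Test occasions (synopsis).** "Cognitive assessment will be completed at baseline and at the end of each phase". Arm B has therefore already been tested twice when its training starts.
- **Entry rule (section 4.2, MCI criteria).** "Objective cognitive impairment is defined as performance of more than or equal to 1.5 standard deviation below the" estimated premorbid level.
- **Source of baseline (section 6.1).** Most baseline tests come from the clinic assessment, and "these data will need to have been collected within the last 6-months in order to be valid for study entry".
- **Retest effects (section 4.2).** "Where possible, alternate forms are used between assessments to reduce retest effects".

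The hypothesis in section 4.2 and Figure 3 is that Arm A's training effect exceeds Arm B's.

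**The concern.** The arms are randomised and so comparable at the same visit. The Phase II model compares them at different visits. Two things differ between the intervals besides the start date of training. Arm A's interval contains the first retest and starts at an assessment on which people were mostly selected for low scores. Arm B's contains a later retest and starts at a visit that selected nobody. If untreated scores drift differently over the two intervals, that difference goes straight into Group by Time.

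The probable direction is the hypothesised one. The model could report a larger effect of early training when the start date makes no difference. Sections 2.3 and 4.2 link the timing question to access and to the allocation of training resources, so a false positive would have practical consequences.

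**Working it through.** **Inputs from the protocol.** The Phase II contrast (synopsis, section 10.3); 52 evaluable participants allocated 1:1, so 26 per arm; within-person correlation 0.4; alpha 0.05 (sections 4.2 and 10.1). **Assumptions, not in the protocol.** Retest gains, regression to the mean, and the drift difference.

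**1. The plan's own figure.** With f = 0.22 and two time points, the noncentrality is f² × N × 2 / (1 − 0.4) = 0.0484 × 52 × 2 / 0.6 = 8.39. Power is 0.811 at N = 52 and 0.795 at N = 50, so 52 reproduces. Then 52 / 0.85 = 61.2, which rounds up to 62. These figures are for Phase I; none is given for Phase II.

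**2. What the interaction estimates.** Let D1 be the untreated change from baseline to FU1 and D2 that from FU1 to FU2. Then

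Group by Time = (effect in A − effect in B) + (D1 − D2).

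D1 contains the first-retest gain plus regression to the mean, less natural decline. D2 contains the second-retest gain, less decline. Arm B's wait-list change estimates D1, but the Phase II model does not use it. No arm shows D2, because over that interval Arm A is past training and Arm B is in training.

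Illustration with assumed first and second retest gains of 0.20 and 0.10 SD, regression of 0.26 SD and no decline: D1 − D2 = 0.20 + 0.26 − 0.10 = +0.36 SD. With retest gains only, it is +0.10 SD.

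**3. False-positive rate when the true effects are equal.** The SD of change is √(2 × (1 − 0.4)) = √1.2 = 1.095. The SE is 1.095 × √(2/26) = 0.304. From the noncentral t on 50 degrees of freedom:

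| Assumed D1 − D2 (SD) | Two-sided rejection | Rejection favouring early start |
|---|---|---|
| 0 | 5.0% | 2.5% |
| 0.1 | 6.2% | 5.1% |
| 0.2 | 9.9% | 9.4% |
| 0.3 | 16.2% | 16.1% |

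If the correlation were 0.7, the SE would be 0.215 and the last column 2.5%, 6.6%, 14.8% and 27.7%.

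**4. The covariate.** With two complete measurements per person, Group by Time is the difference between arms in mean within-person change. A covariate that is constant within a person cancels from that change. In a simulated mixed model with 26 per arm, the interaction was 0.1804 with no covariate, with a separate baseline score, and with the starting score.

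Recast as an analysis of covariance on each arm's own starting score, the simulated bias fell from 0.36 to 0.18 SD, and from 0.10 to 0.04 SD with retest gain only. Adjusting the change score for the common baseline left it at 0.36 SD.

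**5. What the wait-list change can do.** Take Arm A's effect net of Arm B's baseline-to-FU1 change, and subtract an assumed drift d from Arm B's FU1-to-FU2 change. With d equal to Arm B's own earlier drift, the contrast reduces algebraically to the protocol's Phase II contrast. The current model thus assumes equal drift in both intervals. In the illustration, d = 0 gives a bias of −0.10 SD and d = 0.46 gives +0.36 SD. The true value, zero, lies between them.

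**The case against.** **Size.** The protocol gives no drift figure and does not say that the first retest gain exceeds the second. At 0.1 SD the error rate barely moves. This stands, and the range above is only an assumption.

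**Regression to the mean.** A reader might apply the expected return for a single test cut at 1.5 SD below expectation. The protocol does not support carrying that over to the endpoint. Global Cognition (section 8) is a weighted composite of nine scores. Several qualifying tests (Rey Auditory Verbal Learning, Boston Naming, Clock-drawing, Stroop) are not in it, and LOGOS is in it but is not a listed diagnostic test. Diagnosis is by clinician consensus in a referred population, and missing tests are done after consent. A simulation of the entry rule on the composite, with an assumed clinic mean of 0 or −1 SD and a common factor of 25 to 50% of true variance, gave 0.02 to 0.12 SD at retest correlation 0.8 and 0.08 to 0.42 SD at 0.4.

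**Direction.** Baseline data up to 6 months old lengthen Arm A's interval and allow more decline. Section 2.1 calls decline in MCI more rapid, and section 4.2 expects no change or decline on the wait list. Alternate forms also shrink the first-retest gain. This stands, so the direction is probable and not certain.

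**Covariate.** Section 10.3 offers it for differing starting points, not for retest effects, and a SAP could fix its form. That is fair, but as a main effect it does not change the interaction even for starting points, and the analysis-of-covariance form only reduces the bias.

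**Two opposed analyses.** The synopsis also says "Arm A at the end of Phase I will be compared to Arm B at the end of Phase II". A reader might infer that the plan answers one question with two analyses biased in opposite directions. The synopsis places that comparison under Phase III and states no model, and section 10.3 does not carry it. The inference is not supported.

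**Reach.** This is a secondary hypothesis in a trial powered for Phase I. The primary analysis compares the arms at the same occasions and is untouched.

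**Conclusion.** The concern holds in a limited form. The offset in test occasions is in the text, and the failure of a main-effect covariate follows from algebra with complete data. Phase II as specified therefore cannot attribute a difference between the two training effects to the start date. A bias towards early start is probable; it rests on a larger first than second retest gain and on baseline being mostly the qualifying assessment, and decline may offset part of it. Its size cannot be settled from the protocol. The rise in the two-sided false-positive rate from 5% to between 6% and 16% is conditional on an assumed net drift difference of 0.1 to 0.3 SD, 26 per arm and correlation 0.4.

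**What to change.** Amend section 10.3 and the synopsis as follows.

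1. Fit one model to all four visits in both arms, with test occasion as a factor.
2. Estimate Arm A's training effect as the randomised Phase I effect, net of Arm B's baseline-to-FU1 wait-list change.
3. Report Arm B's delayed effect, and its comparison with Arm A's, as non-randomised. Give a stated sensitivity range for untreated drift from FU1 to FU2, for example from zero to Arm B's own baseline-to-FU1 drift. Extend it below zero if net decline is thought plausible.
4. Remove the statement that the covariate controls for different starting points.
5. Do not conclude that early training is better from the Phase II comparison alone. Rest randomised conclusions about timing on the FU3 comparison already planned. That comparison answers the 9-month question and carries unequal time since training. Label any FU2 contrast as mixing timing with waning, since Arm A has then been untrained for three months.

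The cost is analysis wording, with no new visits or data. The downside is that research question b (section 2.2) gets a descriptive answer with a sensitivity range instead of a formal test.

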	
 • Phase III: T-test between Arm A vs Arm B at FU3. • Clinical Response Prediction will be addressed by multiple regression examining relationships between baseline predictor variables (i.e; cognitive profile) and cognitive change scores. • Sample Size and Power This study is powered on the basis of a relative effect size (RES) on Global Cognition of 0.44 at the end of the Phase I RCT (based on average from our Timecourse Trial⁵ and NHMRC SMART trial⁶). Designate power of 0.80 controlling α at 0.05 translates to a required sample size of N=52 (calculated using G*Power 3.1 based on ANOVA repeated measures within-between interaction test, 2 groups, 2 time-points, within subject autocorrelation =0.4, equivalent effect size of [v]=0.22). A sample of N=62 (rounded up from 61) will be recruited to allow for 15% overall attrition (as per Timecourse Trial extrapolated to 9-months).
Duration of the study	3 years

GLOSSARY OF ABBREVIATIONS

ABBREVIATION	TERM
CCT	Computerised Cognitive Training
MCI	Mild Cognitive Impairment
BTS	NHMRC Maintain Your Brain Trial Brain Training System
ADCS-ADL	Alzheimer’s Disease Cooperative Study-Activities of Daily Living
WHOQOL	World Health Organisation Quality of Life
GDS	Geriatric Depression Scale
PSQI	Pittsburgh Sleep Quality Index
APOE 4	Apolipoprotein E 4
BDNF	Brain-derived neurotrophic factor

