The endpoint of FU3 will assess the long-term implication of immediate compared to delayed intervention. If over a 9-month period the timing of a 3-month CCT intervention does not matter, i.e., both arms are cognitively equivalent at the end, then that may influence and inform the distribution of CCT resources in clinics and the community.

Figure 3: Study Hypotheses

Hypotheses

es = effect size

e = endpoint

Primary

Phase I: $es_{A1} > es_{B1}$

Secondary

Phase II: $es_{A1} > es_{B2}$

Phase III: $e_{A3} = e_{B3}$

Assess for eligibility:
Multi-domain MCI criteria
Sleep disturbance criteria
No major neurological/psychiatric/mood disorder

Exclude:
Not meet inclusion criteria
Declined to participate

Written Consent

Enrolment

Baseline Measurements:

- Neuropsychological tests
- Sleep-wake quality
- DNA saliva swab
- Economic decision making

Randomised (n=62)

ARM A
(n=32)

Allocation

ARM B
(n=32)

- Neuropsychological outcomes
- Sleep-wake quality
- Neuroimaging
- Economic decision making
- Review for any adverse events
- Lost to follow-up (reasons)

Follow-up 1
3-months after baseline

- Neuropsychological outcomes
- Sleep-wake quality
- Neuroimaging
- Economic decision making
- Review for any adverse events
- Lost to follow-up (reasons)

- Neuropsychological outcomes
- Sleep-wake quality
- Review for any adverse events
- Lost to follow-up (reasons)

Follow-up 2
6-months after baseline

- Neuropsychological outcomes
- Sleep-wake quality
- Review for any adverse events
- Lost to follow-up (reasons)

- Neuropsychological outcomes
- Sleep-wake quality
- Review for any adverse events
- Lost to follow-up (reasons)

Follow-up 3
9-months after baseline

- Neuropsychological outcomes
- Sleep-wake quality
- Review for any adverse events
- Lost to follow-up (reasons)

- Intention-to-treat analyses: Linear Mixed Model
- Clinical response prediction: Multiple regression
- Excluded from analysis (reasons)

Analysis

- Intention-to-treat analyses: Linear Mixed Model
- Clinical response prediction: Multiple regression
- Excluded from analysis (reasons)

Screening

MCI criteria

MCI is diagnosed according to the Winblad et al 2004 criteria²² confirmed on the basis of consensus rating of multiple clinicians within the memory center.

Typically, this includes a geriatrician or neurologist and two clinical neuropsychologists who review the individual's clinical profile and neuropsychological results.

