8. CLINICAL AND LABORATORY ASSESSMENTS

Primary Outcome Measure

Global Cognition as defined by pre-specified average of z-scores (referenced to baseline) across following weighted cognitive domains:

1. *Memory (40%)*: Wechsler Adult Intelligence Scale (WAIS) Digit Span²⁴; LOGOS; Wechsler Memory Scale-III Logical Memory I²⁶ and II²⁷, Rey Complex Figure Test-3 minute Recall²⁸.
2. *Speed of processing (15%)*: Trails Making A²⁹.
3. *Language (15%)*: Controlled Oral Word Association Test³¹
4. *Visuospatial skills (15%)*: Rey Complex Figure Test-Copy³¹
5. *Executive functioning (15%)*: Trails Making B²⁹

Secondary Outcome Measures

[figure not shown]
1. Individual cognitive domains measured in separate summary z-score composites
2. Daily functional: Amsterdam IADL
3. Quality of life: WHOQOL
4. Mood and mental-health symptoms: 15-Item GDS
5. Sleep-wake patterns: Sleep diary, actigraphy, PSQI
6. Generalised Axiom of Revealed Preferences (GARP⁴¹)
7. Predictors of responsivity: APOE 3/4 and BDNF ValMet polymorphism, baseline cognitive profile and any other baseline descriptor.

Salival DNA Extraction Swabs Protocol

[figure not shown]
A saliva sample will be collected during baseline measurements to examine APOE4 and BDNF ValMet genotype status. DNA samples will be stored in [name] and analyses will be conducted in [name],

[name] by [name]. BDNF Val/Met polymorphism (rs6265) will be analysed using the Taqman SNP BDNF-AS Assay (SNP ID: rs6265).

[figure not shown]
Oragene•DNA (OG-500)

1. Spit into funnel until the amount of liquid saliva (not bubbles) reaches the fill line shown in picture #1.

[figure not shown]
4. Use the small cap to close the tube tightly.

2. Hold the tube upright with one hand. Close the funnel lid with the other hand (as shown) by firmly pushing the lid until you hear a loud click. The liquid in the lid will be released into the tube to mix with the saliva. Make sure that the lid is closed tightly.

5. Shake the capped tube for 5 seconds. Discard or recycle the funnel.

3. Hold the tube upright. Unscrew the funnel from the tube.

Sleep Actigraphy

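### Phase III compares FU3 global cognition without adjusting for baseline: a valid test that gives up precision, with a power cost that depends on a margin the protocol does not state

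*Protocol*

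**What the plan says.** Phase III is described in three places.

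- Protocol, Section 10.3: "Phase III: Equivalence of the two arms at follow up III will be tested using a two one-sided test". No covariate follows.
- Protocol synopsis, statistical procedures: "Phase III: T-test between Arm A vs Arm B at FU3". A two-sample t-test has no covariate.
- Protocol, Section 4.2 and Figure 3: the Phase III hypothesis equates the endpoint levels of the two arms at FU3, whereas Phases I and II compare effect sizes. Section 4.2 says that if timing does not matter, that is, "both arms are cognitively equivalent at the end", the result may inform how training resources are distributed.

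Section 10.3 does set covariates for the other two phases. For Phase I, "Covariates will only be added if baseline differences are noted between groups". For Phase II, "An additional covariate of initial global cognitive status will be added to this analysis".

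The baseline measure exists for everyone. Section 7 schedules the neuropsychological examination at baseline and at all three follow-ups, and Section 6.4 releases the allocation only after all baseline data have been collected. Section 8 expresses the composite as z-scores referenced to baseline. That fixes the scale; it does not subtract or adjust for a participant's own starting value.

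**The concern.** A comparison of follow-up levels leaves in the error term all the between-person variation that baseline could explain. In an equivalence test this matters directly: equivalence is declared only if the whole 90% confidence interval lies inside the margin, so a needlessly wide interval can miss equivalence that is really there.

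The trial is small for this purpose. It is powered for Phase I only (Section 4.2), and 52 participants are assumed to remain after attrition. Phase III is secondary, but it is the analysis meant to say whether early or delayed access leaves people in the same place at 9 months.

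**Working it through.** **Inputs**

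- From Section 10.1: effect size 0.44 (0.22 on the Cohen's f scale), correlation 0.4 for two time points, alpha 0.05, power 0.80, N = 52 required and 62 recruited, 15% attrition. With 1:1 allocation this is 26 per arm after attrition, or 31 per arm with none.
- Assumed, because the protocol does not give them: the equivalence margin (0.44 to 1.0 SD shown), the baseline-to-FU3 correlation ρ (0.3 to 0.5 shown), a one-sided level of 5% for each TOST test, outcome SD of 1, and a true difference of 0.

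**The plan's own figure**

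For the Phase I interaction test, λ = f² × N × 2 / (1 − ρ) = 0.0484 × 52 × 2 / 0.6 = 8.39. The noncentral F with 1 and 50 degrees of freedom gives power 0.811; N = 50 gives 0.795. So 52 is reproduced, and 52 / 0.85 = 61.2, hence 62. No such calculation is given for Phase III.

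**Precision at 26 per arm, ρ = 0.4**

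- Unadjusted: SE = √(2/26) = 0.277 SD. The 90% interval half-width is 1.676 × 0.277 = 0.46 SD.
- Adjusted: residual variance is 1 − 0.4² = 0.84, a cut of 16%. Allowing for estimation of the slope, 0.84 × (1 + 1/48) = 0.8575. SE = √(2 × 0.8575/26) = 0.257 SD, and the half-width is 1.677 × 0.257 = 0.43 SD.
- In sample-size terms, 1/0.8575 = 1.17, or about 17% more participants.

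**TOST power at true equality, 26 per arm**

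Power is computed by exact t integration: the probability that the 90% interval lies wholly inside ± margin. Residual variance is 1 with 50 degrees of freedom (unadjusted), or (1 − ρ²)(1 + 1/48) with 49 (adjusted).

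| Margin (SD) | Unadjusted | Adjusted, ρ = 0.4 | Gain, ρ = 0.4 | Gain, ρ = 0.3 | Gain, ρ = 0.5 |
|---|---|---|---|---|---|
| 0.44 | 2.6% | 7.3% | 4.7 | 1.9 | 10.2 |
| 0.5 | 12.2% | 22.0% | 9.7 | 4.4 | 17.9 |
| 0.6 | 37.5% | 49.0% | 11.5 | 5.5 | 19.7 |
| 0.7 | 60.2% | 70.3% | 10.1 | 5.0 | 16.8 |
| 0.8 | 77.0% | 84.6% | 7.6 | 3.9 | 12.2 |
| 0.9 | 88.0% | 93.0% | 5.0 | 2.6 | 7.6 |
| 1.0 | 94.4% | 97.2% | 2.8 | 1.5 | 4.0 |

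Gains are in percentage points, taken before rounding. A hand check by normal approximation, 2Φ(margin/SE − 1.645) − 1, at margin 0.7 without the slope penalty gives 62% unadjusted and 73% adjusted, close to the exact values.

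At 31 per arm, margin 0.5 and ρ = 0.4, power goes from 23.8% to 35.5%. If the synopsis t-test were used instead, its power at 26 per arm to detect a difference of 0.44 SD would go from 34% to 39%.

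**Chance imbalance**

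The SD of a chance baseline difference at 26 per arm is √(2/26) = 0.28 SD. At ρ = 0.4, a baseline gap of 0.3 SD moves the expected FU3 difference by 0.4 × 0.3 = 0.12 SD, less than half of one standard error. This is the same variance that the 16% already counts, seen from another side; it is not a second loss.

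**The case against.** The best case against the point has four parts.

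- **The text is largely silent.** Section 10.3 names a testing procedure, not a model. A TOST can be run on an adjusted difference, and a separate analysis plan, not seen here, could add the covariate. This is fair for the Section 10.3 sentence alone. It is weaker against the whole document: the synopsis names a t-test, and Section 10.3 gives a covariate rule for each of the other two phases.
- **The test is not invalid.** A reader might infer that a gap present at entry biases the early-versus-delayed answer. The documents do not support that. The arms are randomised and compared at the same visit, so the unadjusted difference is unbiased and its standard error already includes chance imbalance.
- **Phase II is not a precedent.** A reader might infer that Section 10.3 is inconsistent, or that Phase III needs adjustment more than Phase II does. Phase II measures Arm A from baseline and Arm B from FU1, so its starting points differ by design, and that is the stated reason for its covariate. Phase III has only chance differences.
- **The size is uncertain.** No margin is stated, and 0.4 is a two-time-point figure for Phase I. Section 6.1 accepts clinic baseline tests up to 6 months old, which could lower the correlation with FU3. At small margins power stays poor even after adjustment.

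The last three stand in full. They limit the point to precision and its size to a range, but do not remove it.

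**Conclusion.** The point holds as a loss of precision in a secondary analysis. As written, Phase III is an unadjusted comparison of FU3 levels although a baseline value is available for everyone. Adjustment would cut residual variance by about 16% if ρ = 0.4 carries over to 9 months.

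A reader might take one power figure, such as a loss of 8 to 11 points, as established. It is not: it needs a margin between about 0.5 and 0.8 SD, which the protocol does not state, together with ρ = 0.4. Across margins of 0.44 to 1.0 SD at 26 per arm, the gain is about 3 to 11.5 points at ρ = 0.4 and 1.5 to 5.5 points at ρ = 0.3. At ρ = 0.5 it is 4 to 20 points.

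The absent margin and the conflict between the t-test and the TOST are separate matters. Resolving both would leave this one in place.

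**What to change.** In Section 10.3 and the synopsis, define the Phase III estimate as the arm difference at FU3 from a model of FU3 global cognition on arm and baseline global cognition. Run the TOST on the 90% confidence interval of that adjusted difference. Fix the covariate in advance, whatever imbalance is observed, so that the conditional Phase I rule is not carried over. Report the unadjusted comparison as supportive.

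The cost is one sentence in each place and one degree of freedom. No new data, visits or participants are needed.

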3.2 Secondary Objectives

Determine the following:

1. Does the therapeutic cognitive effect differ if training commenced immediately or 3-months later?
2. Does the cognitive state 9-months after entering the trial differ if CCT was commenced immediately or 3-months later?
3. Change in individual cognitive domains measured in separate summary z-score composites
4. Change in daily functional: Amsterdam IADL
5. Change in quality of life: WHOQOL
6. Change in mood and mental-health symptoms: 15-Item GDS
7. Change in sleep-wake patterns: Sleep diary, actigraphy, PSQI
8. Change in risk-perception: Economic Decision Making Competency tool
9. Predictors of cognitive response to CCT: APOE 3/4 and BDNF ValMet polymorphism and baseline cognitive profile.

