10. STATISTICAL METHODS

10.1 Sample Size Estimation

This study is powered on the basis of a relative effect size (RES) on Global Cognition of 0.44 at the end of the Phase I RCT (based on average from our Timecourse Trial⁵ and NHMRC SMART trial⁶). Designate power of 0.80 controlling α at 0.05 translates to a required sample size of N=52 (calculated using G*Power 3.1 based on ANOVA repeated measures within-between interaction test, 2 groups, 2 time-points, within subject autocorrelation =0.4, equivalent effect size of $[\eta^2]=0.22$). A sample of N=62 (rounded up from 61) will be recruited to allow for 15% overall attrition (as per Timecourse Trial extrapolated to 9-months).

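### The protocol is inconsistent on whether the Phase III comparison comes from the intention-to-treat mixed model or from a single-visit test at FU3 that would leave out participants without an FU3 score

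*Protocol*

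**What the plan says.** Section 3.2 of the protocol asks as a secondary objective: "Does the cognitive state 9-months after entering the trial differ if CCT was commenced immediately or 3-months later". Section 4.2 adds that a finding that "both arms are cognitively equivalent at the end" may guide how training resources are allocated. Three places describe how this is to be analysed:

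- **Flow chart (Section 4.2, Figure 3).** The Analysis box follows Follow-up 3, appears in both arm columns and reads "Intention-to-treat analyses: Linear Mixed Model". No phase is named.
- **Synopsis.** The Phase III entry is "T-test between Arm A vs Arm B at FU3".
- **Section 10.3.** "Equivalence of the two arms at follow up III will be tested using a two one-sided test". The intention-to-treat label appears for Phase I only, with an "approach using recommended Linear Mixed Modelling⁴ will evaluate a model including main effects for Group (Arm A vs Arm B), Time (BL vs FU1"). Phase II also has a mixed model. Phase III has neither label.

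Section 10.1 sets the recruitment target "to allow for 15% overall attrition (as per Timecourse Trial extrapolated to 9-months"). Section 6.7 says losses are documented and not replaced. Section 10.2 describes the patients clinically and does not define an analysis set. Cognition is measured at baseline and at the end of each phase, so each participant can contribute up to four scores.

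**The concern.** A t-test at one visit uses only the people seen at that visit. A participant who completes baseline, FU1 and FU2 and then leaves adds nothing to it. A mixed model over all visits keeps that participant in the assigned arm. The two methods therefore answer the 9-month question in different sets of people, and the protocol points to both.

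This matters because the comparison is meant to inform whether early or delayed training should guide resource use. If those who leave differ from those who stay, and differ in another way in the other arm, the arms can look equivalent or different at FU3 because of who remained.

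**Working it through.** **1. The plan's own figures.** Section 10.1 gives f = 0.22, two groups, m = 2 time-points, correlation ρ = 0.4, α = 0.05 and power 0.80. For the within-between interaction, λ = f²·N·m/(1−ρ) = 0.0484 × 52 × 2 / 0.6 = 8.39, with 1 and 50 degrees of freedom. Power is 0.811 at N = 52 and 0.795 at N = 50, so 52 reproduces. Then 52/0.85 = 61.2, rounded up to 62, which also reproduces. Nothing below changes this Phase I calculation.

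**2. Who would be missing at FU3.** 62 × 0.15 = 9.3 lost and 62 × 0.85 = 52.7 observed, or about 9 absent and 53 present (31 × 0.85 = 26.35 per arm).

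**3. The passages side by side.**

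| Place | Method for Phase III | Intention-to-treat stated? |
|---|---|---|
| Flow chart | Linear mixed model | Yes, no phase limit |
| Synopsis | t-test at FU3 | No |
| Section 10.3 | Two one-sided tests at FU3, estimator not named | No (named for Phase I only) |

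The flow chart and the synopsis cannot both describe Phase III. Section 10.3 can be read with either.

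**4. Size of a possible bias.** The protocol gives no dropout pattern, so this is a simulation under assumptions: four visits with equal correlation ρ, no true arm difference, and loss before FU3 depending on the FU2 score through a logistic model with slope 1.5 per SD. ρ = 0.4 is the protocol's value; 0.7 is an assumed higher value. The entries are the spurious FU3 arm difference in SD among those observed:

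| Dropout pattern (assumed) | ρ = 0.4 | ρ = 0.7 |
|---|---|---|
| 15% in each arm, random | 0.00 | 0.00 |
| 15% in each arm, low scorers leave both | 0.00 | 0.00 |
| 20% vs 10%, low scorers leave both | 0.04 | 0.07 |
| 15% in each arm, low scorers leave one, random in the other | 0.07 | 0.12 |
| 15% in each arm, low scorers leave one, high scorers leave the other | 0.14 | 0.24 |

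A second simulation had 31 per arm and 5 lost in each. Loss followed FU1 and FU2 scores plus noise in one arm and was random in the other. It gave 0.11 SD at ρ = 0.4 and 0.16 SD at ρ = 0.6. In every pattern the estimate using the earlier visits was within 0.005 SD of zero. That is expected by construction, because dropout was generated from scores the model sees.

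**5. Precision at ρ = 0.4.** These are large-sample standard errors in SD units.

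- Observed cases only: √(2/26.35) = 0.276.
- All visits, by arm: the share of FU3 variance explained by three earlier visits is R² = 3ρ²/(1+2ρ) = 0.48/1.8 = 0.267. Variance per arm = 0.267/31 + 0.733/26.35 = 0.0086 + 0.0278 = 0.0364, so SE = √(2 × 0.0364) = 0.270.
- All visits with a common baseline mean: subtract ρ²/31 = 0.16/31 = 0.0052, leaving 0.0312 per arm, so SE = √(2 × 0.0312) = 0.250.

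Simulation at the trial's size is less favourable: 0.280 against 0.277 without the baseline constraint, so no gain, and about 0.26 with it. The precision gain therefore comes mainly from the constraint. Section 6.4 supports the constraint, since allocation is disclosed after baseline data are complete.

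**The case against.** Four points can be made against this, and most of them stand in part.

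- **Section 10.3 does not say that anyone is discarded.** A reader might infer that everyone lost by 9 months is dropped. The sentence names no estimator or analysis set. Two one-sided tests are a decision rule and can be applied to an FU3 contrast from a mixed model, which would make 10.3 and the flow chart compatible. This stands. The single-visit reading rests on the synopsis t-test and on the absence of a mixed model in the Phase III sentence.
- **Handling of missing scores for a secondary endpoint can be left to a statistical analysis plan that is not shown.** This stands as to silence. It does not remove the conflict between the flow chart and the synopsis, which is in the protocol's own text.
- **The flow chart also lists "Excluded from analysis (reasons").** A reader might take this as contradicting intention-to-treat. It does not: it is a field to be filled in on a participant flow diagram, next to the one for losses, and it plans no exclusion.
- **Dropout that differs by arm is assumed.** A reader might infer that Arm A will lose more people or different people, because by FU3 it has been without training for 6 months against 3 for Arm B. The protocol does not say so. Its listed reasons for withdrawal in Section 6.7 are not specific to an arm, and Arm B's wait could work the other way. This stands, so the bias figures show what could happen and are not forecasts. Even the adverse 0.11 SD is only about 0.4 of its standard error (0.11/0.28).

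**Conclusion.** The point holds as an inconsistency with a conditional consequence. The flow chart promises an intention-to-treat mixed model for the analysis after FU3; the synopsis states a t-test at FU3; Section 10.3 states an equivalence test at FU3 without saying what it is applied to. Taken at its word, the synopsis method leaves out about 9 of 62 participants and their earlier scores.

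The bias is roughly 0.1 to 0.2 SD if dropout depends on earlier scores differently in the two arms, smaller (0.04 to 0.07 SD) if only the rates differ, and about zero if mechanism and rate are alike. In that last case the cost is precision alone. These figures assume 15% attrition, equal correlation between visits of 0.4 to 0.7, and dropout driven by observed scores. The documents do not show that completer bias will occur. Phase I, the primary outcome and the sample size are not touched. A correction is still worthwhile because it uses data already being collected and costs almost nothing.

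**What to change.** - In Section 10.3 and the synopsis, state that the Phase III equivalence test is applied to the FU3 arm contrast and its 90% confidence interval (each one-sided test at 0.05) from a mixed model of BL, FU1, FU2 and FU3 in all randomised participants by assigned arm, with baseline means held equal across arms.
- In Section 10.2, define that analysis population as all randomised participants.
- Replace the synopsis t-test so that it agrees with Section 10.3 and the flow chart.
- Keep the observed-case FU3 test as a sensitivity analysis.
- If an observed-case test is what is intended, say so and correct the flow chart instead.

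The cost is wording only: no new visits, data or participants. The model relies on dropout being explained by observed scores, which cannot be verified from the data but is a weaker assumption than the completer test makes.
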